6.3.2.1 Dexamethasone: Dose Reduction Levels

Three dose reduction levels are defined for dexamethasone based on the age of subjects, as shown in Table 8. Dose reductions are permanent, dose must not be increased following a dose reduction.

Table 8. Dose Decrements for Dexamethasone

Subject Age	Nominal Dose (mg)	Reduced Weekly Dexamethasone Doses (mg)		
		Dose -1	Dose -2	Dose -3
≤ 75 years	40	20	12 ^a	8 ^b
> 75 years	20	12 ^a	8	-

^a If the dose needs to be divided over 2 days, administer 8 mg on the first day and 4 mg on the second day.

^b The third dose reduction is for subjects 75 years old or younger with steroid intolerance.

6.3.2.2 Dexamethasone: Guidelines for Dexamethasone-related Toxicity

Dexamethasone will be permanently discontinued after **3 dose reductions in subjects who are ≤ 75 years in the event of additional dexamethasone-related toxicities.**

Dexamethasone will be permanently discontinued after 2 dose reductions in subjects who are > 75 years in the event of additional dexamethasone-related toxicities. At the investigator's discretion, dexamethasone may be tapered prior to complete discontinuation according to institutional practice. The subject may continue on treatment with the other protocol-specified drug(s).

Guidelines for dexamethasone-related toxicities are summarized in [Table 9](#).

Table 9. Treatment Guidelines for Dexamethasone-related Toxicity

Symptom	Findings	Recommended Action
Cardiovascular	Edema > grade 3 (anasarca or limiting function and unresponsive to therapy)	
 • Diuretics as needed, and restart dexamethasone at 1 dose decrement; if edema persists despite above measures, decrease dose by another dose decrement. • Discontinue dexamethasone permanently if symptoms persist despite second reduction.
Gastrointestinal Toxicity	Dyspepsia, gastric or duodenal ulcer, or gastritis grade 1 or 2 (requiring medical management)	
 • Continue dexamethasone at same dose and treat with therapeutic doses of histamine 2 (H2) blockers, or proton pump inhibitor. • Consider adding sucralfate or other antiulcer treatment as clinically indicated. • If symptoms persist despite above measures, decrease dexamethasone dose by 1 dose level.
	Dyspepsia, gastric or duodenal ulcer, or gastritis ≥ grade 3 (requiring hospitalization or surgery)	
 • Hold dexamethasone until symptoms return to baseline. • Restart dexamethasone at 1 dose decrement along with concurrent therapy with H2 blockers, sucralfate, or omeprazole. • If symptoms persist despite above measures, discontinue dexamethasone permanently.
	Acute pancreatitis	
 • Discontinue dexamethasone permanently.

Table 9. Treatment Guidelines for Dexamethasone-related Toxicity

Symptom	Findings	Recommended Action
General Disorders	Limb edema > grade 3 (> 30% limb discrepancy in volume; gross deviation from normal anatomic contour; limiting self-care activities of daily living)	
 Hold dexamethasone until symptoms return to baseline. Diuretics as needed, and restart dexamethasone at 1 dose decrement; if edema persists despite above measures, decrease dose by another dose decrement. Discontinue dexamethasone permanently if symptoms persist despite second reduction.
Psychiatric Disorders	Confusion or mood alteration ≥ grade 2 (interfering with function ± interfering with activities of daily living)	
 Hold dexamethasone until symptoms return to baseline. Restart dexamethasone at 1 dose decrement. If symptoms persist despite above measures, reduce by another dose decrement.
Musculoskeletal	Muscle weakness ≥ grade 2 (symptomatic and interfering with function ± interfering with activities of daily living)	
 Decrease dexamethasone by 1 dose decrement. If weakness persists, decrease dose by another dose decrement. Discontinue dexamethasone permanently if symptoms persist.
Metabolism and Nutrition Disorders	Hyperglycemia ≥ grade 3 (fasting glucose > 250 mg/dL)	
 Treat with insulin or other hypoglycemic agents as needed until glucose is ≤ grade 2 (< 250 mg/dL) then resume dexamethasone. If uncontrolled despite above measures, decrease dose by 1 dose decrement until ≤ grade 2 (< 250 mg/dL).
All Other	Other toxicity ≥ grade 3 felt related to dexamethasone	
 Hold dexamethasone dose. Resume at 1 dose decrement when toxicity has resolved to ≤ grade 2. If toxicity recurs, hold dexamethasone dose until toxicity has resolved to ≤ grade 2 and resume dexamethasone dose by another dose decrement. If toxicity recurs despite 2 dose decrements, discontinue dexamethasone permanently.

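### For subjects aged 75 or younger, four rows of Table 9 stop dexamethasone when the same toxicity persists or recurs after two reductions, while Section 6.3.2.2 stops it only after three

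*Protocol*

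**What the plan says.** Protocol Section 6.3.2.1 sets out the dose levels: "Three dose reduction levels are defined for dexamethasone based on the age of subjects, as shown in Table 8". In Table 8, subjects aged 75 or younger start at 40 mg/week and can go to 20, 12 and 8 mg/week. Subjects over 75 start at 20 mg/week and have two reduced levels, 12 and 8 mg/week. Footnote b adds: "The third dose reduction is for subjects 75 years old or younger with steroid intolerance". Reductions may not be reversed.

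The general stopping rule is in the text of Section 6.3.2.2 and depends on age. In the younger group permanent discontinuation comes after "3 dose reductions in subjects who are ≤ 75 years in the event of additional dexamethasone-related toxicities". For the older group: "Dexamethasone will be permanently discontinued after 2 dose reductions in subjects who are > 75 years in the event of additional dexamethasone-related toxicities".

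Table 9, in the same section, gives actions by symptom and does not mention age. The cardiovascular edema and limb edema rows both say "Discontinue dexamethasone permanently if symptoms persist despite second reduction". The muscle weakness row gives two decrements and then says "Discontinue dexamethasone permanently if symptoms persist". The All Other row, for any unlisted dexamethasone-related toxicity of grade 3 or higher, says "If toxicity recurs despite 2 dose decrements, discontinue dexamethasone permanently".

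**The concern.** In these four rows Table 9 follows the two-step ladder that Section 6.3.2.2 reserves for subjects over 75. A subject aged 75 or younger who is already at the second reduced level, and whose same toxicity persists or comes back, is sent down one more level by one passage and taken off the drug for good by the other. The All Other row is itself the general case, so this is more than a few symptom-specific exceptions.

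Dexamethasone is given in both arms and, in the KdD arm, also serves as daratumumab premedication. Investigators who rely on different passages would manage like subjects differently. The dexamethasone exposure, dose-modification and discontinuation summaries would then partly reflect which passage was followed.

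**Working it through.** The plan gives no figure to reproduce. The check sets the passages side by side and counts.

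**1. The ladder (Table 8).** Age 75 or younger: 40 → 20 → 12 → 8 mg/week, three reductions. Over 75: 20 → 12 → 8 mg/week, two reductions. Table 8 lists levels only; the stopping rule is in the text of Section 6.3.2.2.

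**2. The nine rows of Table 9.**

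| Row | Decrements given | Permanent stop stated? |
|---|---|---|
| Cardiovascular edema (> grade 3) | 2 | yes, after the second |
| GI, grade 1 or 2 | 1 | no |
| GI, grade ≥ 3 | 1 | yes, after the first |
| Acute pancreatitis | 0 | yes, at once |
| Limb edema (> grade 3) | 2 | yes, after the second |
| Confusion or mood alteration | 2 | no |
| Muscle weakness | 2 | yes, after the second |
| Hyperglycemia | 1 | no |
| All Other (grade ≥ 3) | 2 | yes, after the second |

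Four rows stop after two decrements, two stop earlier and three state no stop (4 + 2 + 3 = 9). Rows giving a third decrement: 0 of 9.

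**3. One toxicity, by age group.** Take a subject at the second reduced level whose toxicity falls in one of the four rows and persists or recurs.

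- Over 75 (8 mg/week): Section 6.3.2.2 stops and Table 9 stops. They agree.
- 75 or younger (12 mg/week): Section 6.3.2.2 does not yet stop, and Table 8 has 8 mg/week left for steroid intolerance. Table 9 stops. They disagree.

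**4. Several toxicities.** If each row's count applies to its own toxicity, decrements from different rows add up, because reductions are permanent. There are 9 × 8 / 2 = 36 pairs of rows. Five rows give two decrements, three give one and one gives none. Pairs totalling at least three decrements: (5 × 4 / 2) + (5 × 3) = 10 + 15 = 25. For example, one decrement for hyperglycemia plus two for mood alteration makes three. The mood row says only "If symptoms persist despite above measures, reduce by another dose decrement" at its second step, and neither row states a stop. So the third level is reachable across toxicities, though not within one. The protocol does not say whether counts are per toxicity or cumulative.

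**5. What the choice does to a reported summary.** SAP Section 5 defines relative dose intensity as actual dose per week divided by planned dose per week, with both periods ending at the last dexamethasone dose. SAP Section 9.6.7 summarizes it by arm. The planned dose at age 75 or younger is 40 mg/week. As an illustration, assume a Kd subject with 12 weeks at each of 40, 20 and 12 mg/week and no held or missed doses:

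- Stop there: 12 × (40 + 20 + 12) = 864 mg; 864 / (36 × 40) = 864 / 1440 = 60%.
- 4 more weeks at 8 mg: (864 + 32) / (40 × 40) = 896 / 1600 = 56%.
- 12 more weeks at 8 mg: (864 + 96) / (48 × 40) = 960 / 1920 = 50%.
- 24 more weeks at 8 mg: (864 + 192) / (60 × 40) = 1056 / 2400 = 44%.

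The same subject shows a higher relative dose intensity if stopped than if kept on the third level, and moves from a reduction to a discontinuation. The durations are assumed; the documents give none.

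**The case against.** The best defence is that the passages do different jobs: Section 6.3.2.2 sets a ceiling on total reductions, and Table 9 governs a single toxicity that will not settle. The pancreatitis and GI grade ≥ 3 rows show that Table 9 can stop some subjects before any ceiling. Footnote b limits the third level to steroid intolerance, so it need not be a routine step. Table 9 is headed as guidance with recommended actions, and its two edema rows apply only above grade 3.

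Much of this stands as description, but it does not remove the conflict. The ceiling reading is stated nowhere, and no order of precedence is given. The All Other row is not a symptom-specific exception. Section 6.6 refers sites to Table 9 for stopping and rechallenge requirements in hepatic abnormalities, and Table 9 has no hepatic row, so a dexamethasone-related event of grade 3 or higher falls under All Other. Even on the ceiling reading, a younger subject with one recurrent toxicity in these rows never receives the level that footnote b describes.

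A reader might infer three stronger things that the documents do not support:

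- That Table 9 as a whole stops after two reductions, or makes the third level unreachable. Steps 2 and 4 of the working show otherwise.
- That every affected subject differs by 8 mg against 0 mg. In KdD, Section 6.3.2 has separate premedication text for subjects reduced to 20 mg/week, which complicates the actual dose on daratumumab days.
- That the comparison of arms is compromised. The same tables apply to both arms. Primary PFS is assessed by the blinded review committee in all randomized subjects, stopping dexamethasone is not a censoring event in SAP Table 1, and subjects may continue the other drugs. Exposure is summarized descriptively, and the reason for each dexamethasone dose change is recorded.

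Amendment 6 also postdates the meeting of the primary endpoint, which limits the practical gain. It does allow longer treatment, so the text still governs subjects on therapy.

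**Conclusion.** The inconsistency is real and narrow. For subjects aged 75 or younger with the same toxicity persisting or recurring after two reductions, four of nine rows of Table 9 conflict with the text of Section 6.3.2.2 and the third level in Table 8. For subjects over 75 those rows agree with the text. The nominal size is one dose level, 8 mg/week against permanent discontinuation, subject to the KdD premedication text. How many subjects it touches cannot be derived from the documents.

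The consequence is for dexamethasone management and for descriptive exposure, dose-modification and discontinuation summaries. No effect on PFS and no loss of comparability between arms is shown. The conclusion rests on reading the current text as it stands, with no unstated precedence between the passages. It takes no view on which rule is clinically right. The text should be corrected.

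**What to change.** Reconcile Table 9 with Section 6.3.2.2 and Table 8:

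- State, by age group, the number of reductions after which dexamethasone is permanently stopped, and use it in the cardiovascular edema, limb edema, muscle weakness and All Other rows.
- State whether reductions are counted per toxicity or cumulatively.
- Name in Section 6.3.2.2 any row intended to stop earlier than the general rule.

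The clinical team must decide which rule governs. The cost is a wording change in one table and one paragraph, with no added procedures or data collection.

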6.4 Conditions Not Requiring Dose Reduction

Carfilzomib, daratumumab, and dexamethasone do not need to be held in the following cases:

- grade 3 nausea, vomiting, or diarrhea (that responds within 7 days to adequate treatment of antiemetics and/or antidiarrheal agents)
- grade 3 dexamethasone-related hyperglycemia
- isolated grade 3 γ -glutamyl transferase elevation
- grade 3 fatigue (unless persisting for > 7 days)
- alopecia
- hypogammaglobulinemia

6.4.1 Medical Devices

No investigational medical devices will be used in the conduct of this study.

Other non-investigational medical devices may be used in the conduct of this study as part of standard care.

Non-Amgen non-investigational medical devices (eg, syringes, sterile needles), that are commercially available are not usually provided or reimbursed by Amgen (except, for example, if required by local regulation). The investigator will be responsible for obtaining supplies of these devices.

6.5 Other Protocol-required Therapies

All other protocol-required therapies listed below are commercially available and will not be provided or reimbursed by Amgen (except if required by local regulation). The Investigator will be responsible for obtaining supplies of these protocol-required therapies.

6.5.1 Antiviral Prophylaxis

An antiviral is required concomitant medication for the duration of treatment with carfilzomib. Acyclovir (eg, 400 mg PO 3 times a day, or 800 mg PO 2 times a day or per institutional standards), famcyclovir (eg, 125 mg PO given 3 days, twice a day or per institutional standards), or valacyclovir (eg, 500 mg PO, twice a day or per institutional standards), dose adjustments for renal function where appropriate, initiated within 1 week of the first dose should continue for the duration of treatment with carfilzomib and/or daratumumab.

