6.2.1.1 Carfilzomib: Dosage, Administration, and Schedule

Carfilzomib will be administered as an IV infusion. On days when more than 1 investigational product is administered, the required order of administration is as follows: dexamethasone, pre-infusion medications for daratumumab, carfilzomib, daratumumab, and post-infusion medications for daratumumab. Subjects in arm 1 do not require prehydration, however, prehydration can be administered at investigator's

discretion on cycle 1 day 9 and cycle 1 day 16. Mechanical infusion pumps are recommended, but gravity-dependent infusions are permitted if the 30-minute infusion duration can be reliably maintained. For patients with baseline chronic hepatic impairment (mild, moderate), reduce the starting and subsequent doses of carfilzomib by 25% (ie, 15 mg/m² day 1 and 2 of cycle 1 and 42 mg/m² day 8 cycle 1 and thereafter). In case of resolution of hepatic abnormalities, dose escalation may be considered.

Carfilzomib will be dosed twice weekly over 30 ± 5 minutes, on days 1, 2, 8, 9, 15, and 16 of each 28-day cycle. The administration may be within ± 2 days for each scheduled dose. The dose will be 20 mg/m² on cycle 1 days 1 and 2 and 56 mg/m² beginning on cycle 1 day 8 and thereafter. See [Table 13](#) and [Table 14](#) to review the arm 1 and arm 2 dosing schedules, respectively.

Each subject's first dose of carfilzomib will be calculated based upon baseline body surface area (BSA) using the Mosteller formula. In subjects with BSA of greater than 2.2 m², the dose should be capped based on a BSA of 2.2 m². The dose for each subject should not be revised unless the subject experiences a change in body weight of > 20% in which case the BSA and dose should be recalculated. The dose can also be modified in response to toxicity following the dose modification guideline tables.

The planned dose (mg/m²), dose (mg), start date/time, stop date/time, reason for change in planned dose, reason for dose change/withheld, reason for dose delay, reason for dose interruption and package lot number of carfilzomib is to be recorded on each subject's electronic case report form (eCRF).

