6.2.1.1.1 Intravenous Prehydration

Subjects in arm 2 will receive IV prehydration prior to each carfilzomib infusion during cycle 1. For subjects in arm 1, no prehydration for carfilzomib will be required on days of daratumumab administration.

Prehydration will consist of 250 mL normal saline or other appropriate IV fluid.

Thereafter, carfilzomib prehydration should only be administered if the subject's condition and/or risk factors require it. The total volume of prehydration and the reason for prehydration after cycle 1 will be recorded.

6.2.1.2 Carfilzomib: Dosage Adjustments, Delays, Rules for Withholding or Restarting, Permanent Discontinuation

Carfilzomib may be discontinued, temporarily delayed, or dosage temporarily reduced, in the event of a treatment-related toxicity that, in the opinion of the investigator, warrants

the discontinuation, temporary delay or dose reduction, as indicated in [Table 3](#) and [Table 4](#). The subject will be considered on protocol treatment while receiving either carfilzomib or daratumumab (ie, if either carfilzomib or daratumumab are discontinued or interrupted, the subject is still considered on treatment if still taking the other investigational product).

If day 1 of a cycle is delayed, all subsequent doses within the cycle and also day 1 of subsequent cycles should be adjusted accordingly to maintain the 28-day cycle duration. However, if a within-cycle dose is delayed, then the dates of the subsequent within-cycle doses should not be adjusted. For within-cycle doses, if administration does not commence within the allowable window of the scheduled administration date, then the dose will be considered a missed dose. Administration may resume at the next planned dosing date. A missed dose will not be made up.

Carfilzomib must be discontinued permanently if a delay of more than 6 weeks is required due to unresolved toxicity.

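### Protocol Section 6.5.1 gives two durations for the required antiviral prophylaxis, and its famciclovir example conflicts with the continuation instruction in the same sentence

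*Protocol*

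**What the plan says.** Protocol Section 6.5.1 (Antiviral Prophylaxis) sits under Section 6.5, which covers therapies that the protocol requires in addition to study treatment. It has two sentences.

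- The first sets the requirement: "An antiviral is required concomitant medication for the duration of treatment with carfilzomib".
- The second names three drugs, gives an example regimen for each, and says how long they run: "initiated within 1 week of the first dose should continue for the duration of treatment with carfilzomib and/or daratumumab".

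The example regimens in the second sentence are:

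- acyclovir: "Acyclovir (eg, 400 mg PO 3 times a day, or 800 mg PO 2 times a day or per institutional standards"
- famciclovir: "famcyclovir (eg, 125 mg PO given 3 days, twice a day or per institutional standards"
- valacyclovir: "valacyclovir (eg, 500 mg PO, twice a day or per institutional standards"

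Section 6.2.1.2, on carfilzomib dose adjustment and discontinuation, says: "The subject will be considered on protocol treatment while receiving either carfilzomib or daratumumab". Section 6.2.2.2 says the same from the daratumumab side.

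**The concern.** There are two separate conflicts in one short paragraph.

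First, the two sentences attach the antiviral to different treatment periods. Once a KdD subject has stopped carfilzomib and continues daratumumab, the first sentence no longer applies and the second still does. The strength of the instruction changes too: the first sentence states a requirement, while the sentence that brings in daratumumab is advisory. A site, or a monitor checking it, cannot tell whether leaving out the antiviral in that period is a protocol deviation.

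Second, the famciclovir example contains a number of days, which does not fit an instruction to continue throughout treatment.

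What is at stake is consistent delivery of a protective therapy that the protocol treats as mandatory. Exclusion criterion 217 goes as far as excluding patients who are hypersensitive to antiviral drugs. The first conflict can arise only in the KdD arm; the second can arise in either arm.

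**Working it through.** No figure in the plan depends on this paragraph, so the check is a comparison of texts.

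**Step 1: can a subject be on daratumumab without carfilzomib?** Yes, in KdD. Sections 6.2.1.2 and 6.2.2.2 keep such a subject on protocol treatment. Section 6.3.2 gives dexamethasone instructions for the time after carfilzomib has been stopped for good. Table 4 and Section 6.2.1.2 list events that end carfilzomib specifically, such as a toxicity delay of more than 6 weeks. The protocol therefore plans for this situation.

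**Step 2: apply each sentence to each treatment state.**

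| Treatment state | First sentence | Last sentence | Same answer? |
|---|---|---|---|
| KdD, on both products | required | should continue | yes |
| KdD, carfilzomib only | required | should continue | yes |
| KdD, daratumumab only | no requirement stated | should continue | no |
| Kd, on carfilzomib | required | should continue | yes |

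Only the third row gives different durations. It is also the only row in which the advisory wording stands without the requirement behind it.

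**Step 3: compare the three example regimens.** Acyclovir and valacyclovir are given as daily frequencies with no number of days. Famciclovir is given as a daily frequency plus 3 days. The continuation clause is the main clause of the sentence and governs all three drugs.

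**Step 4: try the possible readings of the 3 days.** As a single course, it ends within the first of the 28-day cycles set out in Section 6.2.1.1. As 3 days in each week, which is an assumption that the text does not state, it would cover 3/7 = 43% of days. Neither reading amounts to continuing for as long as treatment lasts. The intended meaning cannot be recovered from the documents.

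**Step 5: look for a passage that settles it.** Section 6.5.8 lists antivirals among permitted supportive therapies, so continuing one is allowed, but it gives no duration. Section 6.5.7 concerns hepatitis B prophylaxis and is a separate matter. No other section was found that resolves either conflict.

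**The case against.** The strongest reply is that the paragraph can be followed without harm. The first sentence does not say to stop the antiviral when carfilzomib stops. A site that follows the last sentence satisfies both. The famciclovir regimen is a parenthesis introduced as an example, with institutional standards as an alternative, inside a sentence whose main clause tells the site to continue. To stop after 3 days, a site would have to disregard that clause.

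Much of this stands, and it rules out a stronger reading that a reader might infer: that some subjects would be left without cover for most of treatment. One could calculate that 3 days is 3/28 = 10.7% of a cycle, but that supposes one literal course, never repeated, against the sentence's own instruction. For the other route, any gap would begin only after carfilzomib ends, which need not be most of treatment. Nor do the documents support a claim that infection rates in the KdD arm would shift: they give no figure for this, and viral infection is not a named endpoint in Section 10.1.1.

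The reply does not remove the inconsistency. The institutional-standards alternative qualifies each regimen; it does not say which product's duration governs. Following the last sentence satisfies both, but a site that relies on the first sentence can also claim to have met the stated requirement. The 3 days and the continuation clause remain at odds within one sentence.

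**Conclusion.** Section 6.5.1 is internally inconsistent in two respects and should be corrected. The duration and the force of the instruction differ for KdD subjects who continue daratumumab after stopping carfilzomib. The famciclovir example conflicts with the continuation instruction beside it.

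The supported consequence is limited: sites reading either part in isolation could apply different durations. The number of subjects who reach daratumumab-only treatment is not stated, nor is the number who would receive famciclovir, so the effect cannot be sized. The conclusion rests on the wording alone and assumes nothing about what sites actually did. It has no bearing on the sample size, power, alpha or any planned analysis. It merits attention because this is an operative instruction for a required protective therapy.

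**What to change.** The sponsor should reconcile, within Section 6.5.1:

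- the first and last sentences, so that one duration and one level of obligation apply, stated explicitly for the case in which only one investigational product continues;
- the famciclovir wording and the continuation instruction, so that they no longer conflict.

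Which duration and which regimen apply is a clinical decision for the sponsor, and none is proposed here. The cost is rewording one paragraph in a protocol amendment and telling sites of the change. The SAP needs no change.
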